7.2.1 Other Risks

7.2.1.1 Loss of confidentiality.

• While participating in this project all study records kept electronically will be on encrypted drives and all paper copies will be kept in locked cabinets in a room requiring badge access for entry but there is always the potential some of the subjects information could be stolen.

Risks of Transfusion/Apheresis catheter

- Injury to local structures
- Phlebitis at insertion site
- Air embolism
- Hetamtoma
- Arrhythmia

- Catheter malposition
- Infection
- thrombosis

7.3 Time Period and Grade of AE Capture

The study staff will start recording AE's from the time of the pre-transfusion type-and-cross blood sample until the end of the subject's last visit on week 4. This process will occur twice due to the cross-over design of the study.

7.4 Monitoring and Recording an Adverse Event

Definition. Any clinically relevant deterioration in laboratory assessments in the opinion of the study investigator or other clinical finding determined relevant by the study investigator is considered an AE.

Reporting source. AEs may be spontaneously reported by the patient and/or in response to an open question from study personnel or revealed by observation, physical examination or other diagnostic procedures.

Prior to the trial. Planned hospital admissions or surgical procedures for an illness or disease that existed before the patient was enrolled in the trial are not to be considered AEs unless the condition deteriorated in an unexpected manner during the trial (e.g., surgery was performed earlier or later than planned).

Pretreatment events following signed informed consent. For serious pretreatment events, the investigator must determine both the intensity of the event and the relationship of the event to study procedures.

Treatment events. For serious AEs, the investigator must determine both the intensity of the event and the relationship of the event to study drug administration.

Not serious AEs. For non-serious AEs, the investigator must determine both the intensity of the event and the relationship of the event to study drug administration.

Follow-up of Adverse Events

All adverse events will be followed with appropriate medical management 30 days following the last dose of the study transfusion or until they are resolved, if they are related to the study treatment.

7.4.1 Procedure for Reporting Drug Exposure during Pregnancy and Birth Events

If a woman becomes pregnant, or suspects that she is pregnant, while participating in this study, she must inform the investigator immediately and permanently discontinue study participation. The investigator must notify the DSMC by email. The pregnancy must be followed for the final pregnancy outcome.

7.4.2 Subject Complaints

If a complaint is received by anyone on the study staff, it will be discussed with the study staff and will be addressed on a case-by-case basis. The PI will be notified of any complaints. Complaints will be reported to the IRB if indicated.

If the subject has questions about his or her rights as a study subject, wants to report any problems or complaints, obtain information about the study or offer input, the subject can call the UNC Hospital research subject advocate or the study PI at [contact]. This information is provided to the subject in their consent.

7.4.3 Routine Reporting Procedures for AEs

Study staff must report the Adverse Event form within 7 days of each study transfusion. The Adverse Event Checklist will indicate whether or not one or more of the events listed in Section 8.2 occurred during the transfusion. The PI will be also be notified of the identified event within 24 hours of learning of the event by phone or email.

Since this is an investigator-initiated study, the principal investigator, also referred to as the sponsor-investigator, is responsible for reporting serious adverse events (SAEs) to any regulatory agency and to the sponsor-investigator's IRB. Regardless of expectedness or causality, all SAEs (including serious pretreatment events) must also be reported to the DSMB as soon as possible, but no later than five calendar days after the sponsor-investigator's observation or awareness of the event.

Signs or symptoms reported as adverse events will be graded and recorded by the investigator, according to the CTCAE. When possible, signs and symptoms indicating a common underlying pathology should be noted as one comprehensive event.

The investigator will assess all adverse events and determine reporting requirements to the UNC Safety Monitoring Committee (SMC) and MCW's Institutional Review Board. The investigator will report SAEs to any required regulatory agency and to the sponsor-investigator's IRB.

All adverse events, whether or not unexpected, and whether or not considered to be associated with the use of the study drug, will be entered into the studies AE log.

Reporting to the Safety Monitoring Committee

Regardless of expectedness or causality, all SAEs (including serious pretreatment events) must also be reported to the SMC as soon as possible, but no later than five calendar days of the sponsor-investigator's observation or awareness of the event.

Report Method: The investigator will use email to report SAEs to the SMC. The SAE report must include event term(s), serious criteria and the sponsor-investigator's or sub-investigator's determination of both the intensity of the event(s) and the relationship of the event(s) to study drug administration. Intensity for each SAE, including any lab abnormalities, will be determined by using the NCI CTCAE as a guideline whenever possible.

Reporting to MCW Committee Institutional Review Board

The principal investigator must report events to the MCW IRB within five business days of his/her awareness of the event.

8 INTERVENTION INFORMATION

8.1 Agent #1: Chromium-labeled red cells

8.1.1 Product Description: Chromium-labeled red cells is an FDA approved cross-match compatible red cell transfusion product.

Contraindications: Pregnancy

Side Effects: None known.

Solution Preparation

- 1. Prepare the Cr-51 dose.
- 2. With a 20 gauge needle, withdraw 50 milliter of the unit and immediately transfer syringe contents to the ACD vial using a 25 gauge needle as an airway. Mix gently.
- 3. From the ACD vial, withdraw 4-6 milliliter of whole blood and place in a lavender top tube labelled background.
- 4. Label the red blood cells by adding 200 microcurie of Cr-51 to the ACD vial and mix gently. Incubate at room temperature for 30 minutes, mixing gently every 10 minutes.
- 5. After the 30-minute incubation of Cr-51 with blood, add 50 milligram of ascorbic acid to the ACD vial, mix gently and let stand for 5 minutes.
- 6. Withdraw all of the Cr-51 labelled RBC into a 60 milliliter syringe and inject the patient. Make note of the location of injection.

8.1.2 Investigational Agent Administration

The 51Cr labeled red cells will be infused intravenously (over 1 minute through one IV line) into the subject.

8.1.3 Storage Requirements

The 51Cr labeled red cells will be stored at 1-6° C per standard blood bank storage conditions for red cells.

8.1.5 Route of Administration

The 51Cr labeled red cells will be infused intravenously (over 1 minute through one IV line) into the subject via a midline catheter that is placed by interventional radiology prior to the infusion.

8.1.6 Nursing Implications

The infusion will be provided by a trained assigned staff member of the Nuclear Medicine Department.

8.1.7 Handling

The 51Cr labeled red cells will be stored at 1-6° C per standard blood bank storage conditions for red cells. The prepared red cell product is intended to be infused as soon as the labeling step is complete.

8.1.8 Agent Ordering

The UNC Nuclear Medicine Department will order and create the compound as necessary for this single site study.

9 STATISTICAL CONSIDERATIONS

9.1 Study Measures

9.1.1 Outcome Variables

For Aims 1 and 2, the outcome measures of interest will be obtained from blood samples on 15 occasions within each of Period1 and Period2: At baseline prior to the infusion treatment. Post-infusion at 5, 7.5, 10, 12.5, 15, 30 minutes, and at 1, 24, 48, 72 hours, and at 1, 2, 3, 4 weeks.

For Aim 1, for purposes of the main analysis the measurements of $\frac{51}{CR}$ -labeled PTR of RBCs prior to infusion and at 24 hours post-infusion are of interest. The units of measurement will be % recovery.

For Aim 2a and b, the outcome measures are Hemoglobin A and the following other clinically-relevant measures. We will evaluate their longitudinal tragectories over 4 weeks:

- complete blood count with differential (CBCD: RBCs, WBCs, PLTsHCT, PCV, Hgb, MPV, throbocytes)
- reticulocyte count per RBCs (%),
- Hgb A, Hgb A2, Hgb F (% of total by electrophoresis)
- cell-free hemoglobin (mg/dL),
- haptoglobin (mg/dL),
- Iron (mcg/dL), TIBC (mcg/dL), transferrin saturation (%), ferritin (mcg/L),
- bilirubin values (total, direct, indirect) (mg/dL),
- high-sensitivity C-reactive protein (HSCRP) (mg/L),
- lactate dehydrogenase (LDH) (U/L),
- myeloperoxidase (MPO) (pmol/L),
- labile plasma iron (LPI) (µmol/L)
- non-transferrin bound iron (NTBI) (µmol/L)

Note: normal and valid values of these measurements will be determined by the clinical laboratories performing these assays.

For Aim 2c, the outcomes of interest are the metabolomic profile estimates obtained for each blood sample. The unit of measure will be $(\mu mol/L)$

For Aim 2d, pain scores, occurrence of infection, and antibiotic use will be obtained via a daily 4-week diary for evaluation of pain on an ordinal scale (0,1,2,...,10), occurrence of infection symptoms, and use of antibiotics (type, duration, dose).

9.1.2 Baseline Characteristics of the Participants

At enrollment, the following will be recorded: age, gender, history of past red cell transfusions, red cell phenotype, medical history information, and surgical history information.

9.2 Study Design

For this Phase II, single-blind, controlled trial, the experimental design is a two-treatment, two-period, twosequence cross-over design: CO(2,2,2). The two treatment regimens are

Regimen **A** transfusion of one G6PD-deficient donor units stored 15-25 days

Regimen **B** transfusion of one G6PD-normal donor units stored 15-25 days The two sequences of treatment are **AB** and **BA**. The two 4-week periods will be separated by a 4-month washout interval. We believe the 4-month washout interval will be adequate to prevent carryover effects from period1 into period2 because RBCs normally only survive 120 days (4 months) at their maximum normal survival.

9.3 Randomization, Concealment and Blinding

The two sequences (**AB** and **BA**) will be assigned to the N=16 enrollees as determined by RBC unit availability at the time of the first exchange transfusion. The two 4-week periods will be separated by a 4-month washout interval.

In crossover studies, reliably concealed unit assignment is the basis for the important assumption that 'sequence effects are zero'. Per the CONSORT Statement, allocation concealment will be used to prevent selection bias by concealing the allocations from the study personnel who are responsible for enrolling and assigning participants --until the moment of assignment.

After consent, one RBC unit will be requested for the study transfusion. The study staff member will then contact UNC transfusion service to confirm that the transfusion service has a units that meet the crossmatch requirements (ABO, sickle negative, antigen matched) for this subject. The patient will then be enrolled in the study and assigned to a treatment sequence (**AB** or **BA**) depending upon RBC unit availability. The subject will be contacted regarding the date of their study transfusion once a suitable unit (G6PD deficient or G6PD normal) becomes available, and reaches the appropriate storage age, per protocol.

9.4 Replacement Policy

Replacement of enrolled participants who discontinue the study is not recommended because it be a source of selection bias. It is preferable to choose a target enrollment that is sufficiently large to be able to cope with dropout.

9.5 Accrual Estimates

The Adult Sickle Cell Disease clinic at UNC sees about 450 patients per year, of which only 50 would be eligible due to being on chronic transfusion. Given known estimates of alloimmunization, 75% of these patients would be eligible to approach for consent (N=37). Due to the complexity of the study, target enrollment will aim for 4-8 research subjects per year, with a 3-4 year timeframe for study completion. Additional sites may be considered at the discretion of the principal investigator to meet enrollment goals.

Uncertainty about the optimal choice of methods and assumptions is best handled by relegating competing approaches to an important role in the domain of sensitivity analyses. The various sensitivity analyses will be used to evaluate the robustness/sensitivity of the study's main results to reasonable perturbations/modifications of the statistical methods and assumptions used. Results of the sensitivity analyses will be used to guide our level of trust in the main results.

[Reference: 2019 ICH E9-R1 addendum, "Estimands and Sensitivity Analysis in Clinical Trials". www.gmp-compliance.org/guidemgr/files/E9-R1_Step4_Guideline_2019_1203.pdf]

Exploratory analyses will be distinguished from confirmatory analyses. The purpose of exploratory analyses will be to generate new hypotheses or to refine hypotheses; p-values will not be used in exploratory analyses.

Statistical computations will be performed using software from Cytel (StatXact and LogXact), SAS Institute (SAS version 9.2), and Salford systems (CART).

Analysis Plan for Aim 1. The longitudinal analysis of the effects of treatment on 24-hour ⁵¹CR-labeled PTR of RBCs will rely on a generalized linear mixed-effects model which expresses mean response as a function of treatment regimen, treatment period, and occasion. The baseline PTR value will be treated as being one of the outcomes. The fitted model will be used to obtain parameter estimates that characterize the 24-hour trajectory of the mean response for each of the two regimens. Graphical figures will be used to display the resulting point- and interval-estimates.

Hypothesis testing. An F-test procedure will be used to test the null hypothesis "the treatment effect is exactly zero in the target population".

Missing data. For this main analysis, all enrollees with at least one post-exchange transfusion evaluation will be included. We anticipate that the main analyses will rely on an assumption that missing data values, if any, are attributable to ignorable causes (i.e., the mechanisms satisfy the "missing at random" (MAR) criteria.)

Sensitivity analyses. After the main analysis has been conducted, sensitivity analyses will be used to evaluate the robustness/fragility of the main results to reasonable perturbations of the statistical methods and assumptions used. Results of the sensitivity analyses will only be used to guide trust in the main results. The sensitivity analyses will include, for example: diagnostics for goodness of fit and influential observations, and analysis of residuals for examination of distributional assumptions; evaluation of the impact of using alternative statistical procedures (for coping with missing values); investigation of the impact of including / excluding questionable data values. As part of the sensitivity analyses, investigation of missing values will include use of logistic regression methods to investigate apparent causes for missing data, and multiple imputations methods. The impact of using alternative assumptions regarding the variance covariance structure will also be included in the sensitivity analyses. The impact of using alternative distributional assumptions and transformations of scales will also be considered.

Auxiliary analyses. Longitudinal analyses of the PTR data spanning all 15 occasions per period will also be performed to characterize the trajectory of the mean response for each regimen over 4 months.

Analysis Plan for Aim 2a. The longitudinal analysis of the effects of treatment on Hemoglobin A will rely on the same analysis strategy as described for Aim 1 for Estimation, Hypothesis testing, handling Missing data, and Sensitivity analyses.

Analysis Plan for Aim 2b. For each of the 26 outcome variables, a longitudinal analysis of the effects of treatment on mean response will rely on an analysis strategy similar to that described in Aim 1 for Estimation. handling Missing data, and Sensitivity analyses. Regardless of scale, the *strategy* for obtaining the main results is the same for each regimen and for the difference between the regimens, point estimates of central

tendency and variance will be obtained along with 95% confidence intervals to indicate precision.

Analysis Plan for Aim 2c. For the purpose of hypothesis generation, exploratory statistical methods (reference: Tukey, 1977) and exploratory predictive modeling methods will be used to investigate associations between *treatment_regimen* and longitudinal metabolomic profiles.

Analysis Plan for Aim 2d. For each of the outcome variables [pain on an ordinal scale {0,1,2,..., 10}, occurrence of infection symptoms, and use of antibiotics (type, duration, dose)], a longitudinal analysis of the effects of treatment on mean response will rely on an analysis strategy similar to that described in Aim 1 for Estimation, handling Missing data, and Sensitivity analyses.

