	For Aim 2c, the outcomes of interest are the metabolomic profile from blood samples obtained longitudinally.						
	For Aim 2d, pain scores , occurrence of infection , and antibiotic use will be obtained via a daily 4-week diary for evaluation of pain on an ordinal scale (0,1,2,,10), occurrence of infection symptoms, and use of antibiotics (type, duration, dose).						

Study Design	For this Phase II, single-blind, longitudinal controlled trial, the experimental design is a two-treatment, two-period, two-sequence cross-over design. The two treatment regimens are (A) infusion of G6PD-deficient donor units, and (B) infusion of G6PD-normal donor units. Due to the scarcity of G6PD-deficient units in the donor pool, we will exchange units that are available at the time of scheduled study exchange (likely normal units) and not utilize a randomization scheme. Each 4-week study exchange period will be separated from the second study exchange by a 4-month washout interval. During the washout period, we will look for suitable units (likely G6PD-deficient) for the second study exchange.
Sample	N = 16 eligible patients will be enrolled
Participation Time	Each enrollee's participation will last at least 6 months
Enrollment Time	Recruitment and enrollment of the participants will require 4 years

SCHEMA

Protocol: Single blind, randomized, crossover study

Figure 1: Study Schema: We will compare two treatment regimens via is a two-treatment, two-period, two-sequence cross-over design: CO(2,2,2). The two treatment regimens are (**A**) infusion of G6PD-deficient donor units, and (**B**) infusion of G6PD-normal donor units. The two sequences (**AB** and **BA**) will be assigned to the N=16 enrollees by RBC unit availability at the time of the first study exchange transfusion.

The two 4-week periods will be separated by a 4-month washout interval. The outcome measures of interest are 24-hour ⁵¹CR-labeled PTR of RBCs, and Hemoglobin A evaluated before and 4 weeks after infusion.

Period/ Procedure					Fo		Follow	-up visits			
Study Day/Visit Day	24-72 hrs pre- infusio n	Pre- transfusio n	5,7.5,10,12.5,15, 30 min post infusion	1 hr post transfusion/ infusion (+/-15 min)	24hr post infusion (+/- 3 hours)	48 hr post infusio n (+/- 3 hours)	72hr post infusio n (+/- 3 hours)	1week post infusio n (+/- 1 day)	2week post infusio n (+/- 2 days)	3 week post infusio n (+/- 2 days)	4 week post infusio n (+/- 2 days)
Informed consent	х										

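### The Aim 1 mixed model has no sequence term, although sequence is set by unit availability; any AB/BA difference can leak into the treatment estimate, usually by a small amount

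*Combined protocol and SAP*

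**What the plan says.** Section 9.6 (Analysis Plan for Aim 1) describes a mixed model that "expresses mean response as a function of treatment regimen, treatment period, and occasion". Sequence is not listed. Aims 2a, 2b and 2d take over the same or a similar strategy. For missing data, "all enrollees with at least one post-exchange transfusion evaluation will be included", under a missing-at-random assumption, so a participant with one period stays in. Section 4.9 says treated participants who leave are not replaced.

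Section 9.3 states that "reliably concealed unit assignment is the basis for the important assumption that" sequence effects are zero. The same section assigns the two sequences "as determined by RBC unit availability at the time of the first exchange transfusion". The Study Design entry of the Protocol Summary says the team will "exchange units that are available at the time of scheduled study exchange (likely normal units) and not utilize a randomization scheme". Section 4.8 adds that deficient units are taken first when in stock, that units must match the recipient's ABO and Rh/Kell type, and that clinical staff can see the arm assignment.

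The overview in 9.6 names the variance under each regimen among the parameters of interest. Section 9.9 quotes SDs of 3.2% (normal) and 8.4% (deficient). The main model's covariance structure is not stated; alternative structures appear among the sensitivity analyses.

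**The concern.** The plan names the condition under which sequence can be ignored and then uses an allocation that does not secure it. Stock on the day decides the order, and stock depends on the recipient's blood type and on calendar time, so the AB and BA groups need not be exchangeable. Even perfect concealment would not make stock-driven allocation random.

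In a crossover with complete pairs, each participant normally serves as his or her own control and a stable group difference cancels. It does not fully cancel if some participants contribute only one regimen, or if the model weights the two regimens unequally and the groups differ in size. Both are plausible here: normal-first participants must wait for the scarcer deficient unit, and the plan expects mostly normal-first starts. Section 9.6 makes the point and interval estimates the main result, so a shift in the estimate matters even where the p-value is safe.

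**Working it through.** **Set-up.** One 24-hour PTR value per participant per period. A is deficient and B is normal, as in Section 9.2. The effect is A minus B; δ is mean PTR in the AB group minus that in the BA group. No document gives δ. I assume 5 points and show 2 points beside it.

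**The plan's own figures.** SD of differences at ρ = 0.5: √(3.2² + 8.4² − 2·0.5·3.2·8.4) = √(10.24 + 70.56 − 26.88) = √53.92 = 7.34, and 7.34/√16 = 1.84 (plan: 7.3 and 1.8). A two-sided paired t-test with 15 df gives power of 99.9%, 78.5%, 72.6% and 28.0%, against the plan's 99%, 78%, 72% and 28%. They reproduce. They assume complete pairs, and this point does not change them.

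**Mechanism.** With a sequence term the four cell means (two sequences by two periods) are unrestricted. Dropping the term forces the sum of the two period means to be equal in AB and BA. Let ĉ be the estimated departure from that, with expectation 2δ. The generalized least squares estimate without the term equals the estimate with it minus [Cov(τ̂, ĉ)/Var(ĉ)]·ĉ, so the bias is −2δ·Cov(τ̂, ĉ)/Var(ĉ).

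**Route (a): single-period participants, common variance, random intercept.** Sequence s has n participants, m of them with both periods and the rest with period 1 only. Let K = 1/n(AB) + 1/n(BA), and let H be the sum over sequences of (1/m − 1/n). Then

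bias = δ(1 − ρ)H / [2K + (1 − ρ)H].

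It does not depend on the SD. With complete pairs H = 0 and the bias is 0. Example: 8:8 with six BA participants lacking period 2 has H = 1/2 − 1/8 = 0.375 and K = 0.25. At ρ = 0.5 the bias is 5·0.1875/(0.5 + 0.1875) = 1.36; at ρ = 0 it is 5·0.375/(0.5 + 0.375) = 2.14.

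| AB:BA, period 1 only | H | K | Bias, δ = 5 (ρ 0.5 to 0) | Bias, δ = 2 |
|---|---|---|---|---|
| 4:12, 3 BA | 0.0278 | 0.3333 | 0.10 to 0.20 | 0.04 to 0.08 |
| 8:8, 3 BA | 0.0750 | 0.2500 | 0.35 to 0.65 | 0.14 to 0.26 |
| 4:12, 1 AB and 3 BA | 0.1111 | 0.3333 | 0.38 to 0.71 | 0.15 to 0.29 |
| 8:8, 6 BA | 0.3750 | 0.2500 | 1.36 to 2.14 | 0.55 to 0.86 |

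**Route (b): all pairs complete, regimen-specific variances.** With covariance ρσ(A)σ(B),

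bias = −δ · [σ(A)² − σ(B)²] / [σ(A)² + σ(B)² + 2ρσ(A)σ(B)] · [n(BA) − n(AB)]/16.

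With SDs 8.4 and 3.2 and ρ = 0.5, the variance ratio is (70.56 − 10.24)/(70.56 + 10.24 + 26.88) = 60.32/107.68 = 0.560. At 4:12 the bias is −5·0.560·8/16 = −1.40; at 2:14 it is −5·0.560·12/16 = −2.10. At δ = 2 these are −0.56 and −0.84. Equal variances or an 8:8 split give zero.

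**With sequence in the model** the expected bias is 0 in every scenario above, provided each sequence keeps at least one completer. A simulation with REML fits (8:8, 1 AB and 3 BA single-period, δ = 5, ρ = 0.5) gave 0.41 without the term and 0.01 with it (Monte Carlo SE 0.13).

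**Cost in standard error** (common SD 7.3 for route (a)). In the first three rows the rise is 1% or less. For 8:8 with six BA lost it is 2.46 to 2.66 at ρ = 0.5 (8%) and 11% at ρ = 0. For route (b) it is 1.95 to 2.12 at 4:12 (9%) and 2.23 to 2.78 at 2:14 (24%).

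**The case against.** The strongest reply is about size. In the pattern the plan makes most likely, mostly normal-first with a few of them never reaching period 2, the bias is 0.10 to 0.20 points, or 5 to 7% of one standard error, against a hypothesized effect of 10. The 5-point difference is an assumption: it exceeds the normal-donor SD of 3.2 and is about three quarters of the 6.8-point effect seen in healthy recipients. The causes suggested for it are conjecture; Section 4.8 ties blood type to unit matching, but nothing ties it to PTR. The number of single-period participants is also assumed, since 9.9 allows only for a few incomplete. All of this stands and keeps the point minor.

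The term is not always free either. At 2:14 with one AB and four BA participants lacking period 2 (δ = 5, ρ = 0.5), root mean squared error is 3.59 with the term and 3.58 without.

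The sensitivity analyses in 9.6 are given as examples and could accommodate a complete-pair analysis. Neither that nor a sequence term is named.

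Three stronger readings are tempting and not supported. A reader might infer that allocation is unconcealed; Section 9.3 asserts concealment, and that availability fails to deliver it is an inference. A reader might infer that the Aim 1 result or its power is undermined; no document shows that the groups differ, and the power figures reproduce. A reader might infer the reverse, that complete pairs always protect the contrast; route (b) shows this holds only with common variance or equal splits.

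**Conclusion.** The point holds as a cheap improvement of low severity. The stated model relies on zero sequence effects, and the plan's own ground for that assumption is not secured by its allocation. The resulting bias is conditional on a real AB/BA difference, plus either single-period data or regimen-specific variances with unequal sequences.

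For an assumed 5-point difference, bias is below about a quarter of a standard error with light dropout. It reaches 55 to 70% of one with six of eight BA participants incomplete, and 72 to 94% under route (b) (1.40/1.95 and 2.10/2.23). At 2 points every figure is 40% as large. The sign follows which group has the higher PTR, and for a given difference the two routes push in opposite directions. Route (b) applies only if the fitted model has regimen-specific variances, which the plan leaves open.

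**What to change.** Add sequence (AB, BA) as a fixed nuisance effect in the Aim 1 model and in the Aim 2 models that copy it. Pre-specify a complete-pair, within-participant estimate as a sensitivity analysis. Do not test the sequence term or use it as a carryover test.

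Before coding, reconcile the regimen labels: Section 9.2 makes A the deficient regimen, while the standard-error table in 9.9 makes A the normal one.

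The cost is one model term and no new data, with the standard-error increases shown above: 1% or less with light dropout, 8 to 11% with six of eight BA participants single-period, and 9 to 24% with regimen-specific variances and unequal splits. The term removes stable group differences only. It does not address carryover, or the near-confounding of period with regimen that would arise if almost everyone started on normal units.
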